Dark chocolate, e.g., Hershey's Dark or Dove Dark			 W				 D			
Candy bars, e.g., Snickers, Milky Way, Reeses			 W				 D			
Candy without chocolate (1 oz.)			 W				 D			
Cookies (1)	Fat free or reduced fat			 W			 D			
Brownies (1)	Other			 W			 D			
Doughnuts (1)	Fat free or reduced fat			 W			 D			
Cake	Other			 W			 D			
Pie, homemade or ready made (slice)			 W			 D				
Jams, jellies, preserves, syrup, or honey (1 Tbs)			 W			 D				
Peanut butter (1 Tbs)			 W			 D				
Popcorn (3 cups)	Fat free or light			 W			 D			
	Regular			 W			 D			
Sweet roll, coffee cake or other pastry (serving)	Fat free or reduced fat			 W			 D			
or other pastry (serving)	Other			 W			 D			
Breakfast bars, e.g., Nutrigrain, granola, Kashi (1)			 W			 D				
Energy bars, e.g., Clif, Luna, Glucerna, Powerbar (1)			 W			 D				
Low carb bars, e.g., Atkins, Zone, South Beach (1)			 W			 D				
Pretzels (1 small bag or serving)			 W			 D				
Peanuts (small packet or 1 oz.)			 W			 D				
Walnuts (1 oz.)			 W			 D				
Other nuts (small packet or 1 oz.)			 W			 D				
Oat bran, added to food (1 Tbs)			 W			 D				
Other bran (wheat, etc.), added to food (1 Tbs)			 W			 D				
Chowder or cream soup (1 cup)			 W			 D				
Ketchup or red chili sauce (1 Tbs)			 W			 D				
Splenda (1 packet)			 W			 D				
Other artificial sweetener (1 packet)			 W			 D				
Olive oil added to food or bread (1 Tbs)			 W			 D				
Low-fat or fat-free mayonnaise (1 Tbs)			 W			 D				
Regular mayonnaise (1 Tbs)			 W			 D				
Salad dressing (1-2 Tbs)			 W			 D				
Type of salad dressing:  Nonfat  Low-fat  Olive oil  Other vegetable oil										
7. Liver: (beef, calf or pork 4 oz.)  Never  Less than 1/mo  1/mo  2-3/mo  1/week or more										
Liver: (chicken or turkey 1 oz.)  Never  Less than 1/mo  1/mo  2-3/mo  1/week or more										
8. How often do you eat fried or sautéed food at home? (Exclude "Pam"-type spray)  Less than once a week  1-3 times per week  4-6 times per week  Daily										
9. What kind of fat is usually used for frying and sautéing at home? (Exclude "Pam"-type spray)  Real butter  Margarine  Olive oil  Vegetable oil  Veg. shortening  Lard  N/A										
10. What kind of fat is usually used for baking at home?  Real butter  Margarine  Olive oil  Vegetable oil  Veg. shortening  Lard  N/A										
11. What type of cooking oil is usually used at home? (e.g., Mazola Corn Oil)  Specify brand and type										
12. How often do you eat deep fried chicken, fish, shrimp, clams or onion rings away from home?  Less than once a week  1-3 times per week  4-6 times per week  Daily										
13. How often do you eat toasted breads, bagel or English muffin (e.g., slice or 1 half bagel)?  Less than once a week  1-3 times per week  4-6 times per week  Daily  2+ times/day										
14. Are there any other important foods that you usually eat at least once per week ? Other foods that you usually eat at least once per week Servings per week										
Include for example: Applesauce, mushrooms, bulgur, radish, horseradish, Eggbeaters, dates, figs, rhubarb, mango, mixed dried fruit, papaya, wheat germ, custard, venison, hot peppers, pickles, olives, SlimFast, Ensure (regular or plus), Glucerna Shake.										
(a)										
(b)										
(c)										

15.5.6 **Profile 29 (v2.0)**

ARA08: StopRA		REQUIRED Source Document		Manual of Procedures	
ARA08 PROMIS-29 REQUIRED SOURCE DOCUMENT Read EDC Page: PROMIS-29					
Subject ID: _____		Assessment Date (DD/MON/YYYY): _____			
Physical Function	Without any difficulty	With a little difficulty	With some difficulty	With much difficulty	Unable to do
1 Are you able to do chores such as vacuuming or yard work?					
2 Are you able to go up and down stairs at a normal pace?					
3 Are you able to go for a walk of at least 15 minutes?					
4 Are you able to run errands and shop?					
Anxiety In the past 7 days...	Never	Rarely	Sometimes	Often	Always
5 I felt fearful...					
6 I found it hard to focus on anything other than my anxiety...					
7 My worries overwhelmed me...					
8 I felt uneasy...					
Depression In the past 7 days...	Never	Rarely	Sometimes	Often	Always
9 I felt worthless...					
10 I felt helpless...					
11 I felt depressed...					
12 I felt hopeless...					
Fatigue During the past 7 days...	Not at all	A little bit	Somewhat	Quite a bit	Very much
13 I feel fatigued...					
14 I have trouble starting things because I am tired...					

ARA08: PROMIS-29

Page 1 of 3

09 SEP 2015

ARA08: StopRA		REQUIRED Source Document					Manual of Procedures	
Fatigue In the past 7 days...		Not at all	A little bit	Somewhat	Quite a bit	Very much		
15	How run-down did you feel on average?							
16	How fatigued were you on average?							
Sleep Disturbance In the past 7 days...		Very poor	Poor	Fair	Good	Very good		
17	My sleep quality was...							
Sleep Disturbance In the past 7 days...		Not at all	A little bit	Somewhat	Quite a bit	Very much		
18	My sleep was refreshing...							
19	I had a problem with my sleep...							
20	I had difficulty falling asleep...							
Ability to Participate in Social Roles and Activities		Never	Rarely	Sometimes	Usually	Always		
21	I have trouble doing all of my regular leisure activities with others...							
22	I have trouble doing all of the family activities that I want to do...							
23	I have trouble doing all of my usual work (include work at home)...							
24	I have trouble doing all of the activities with friends that I want to do...							
Pain Interference In the past 7 days...		Not at all	A little bit	Somewhat	Quite a bit	Very much		
25	How much did pain interfere with your day to day activities?							
26	How much did pain interfere with work around the home?							
27	How much did pain interfere with your ability to participate in social activities?							
28	How much did pain interfere with your household chores?							

ARA08: StopRA	REQUIRED Source Document	Manual of Procedures
Pain Intensity In the past 7 days...		
29 How would you rate your pain on average?	   	0 1 2 3 4 5 6 7 8 9 10
	No pain	Worst imaginable pain
Subject Initials: _____		Date survey completed: _____ (DD/MON/ YYYY)
ARA08: PROMIS-29 Page 3 of 3 09 SEP 2015

1. LIST OF ABBREVIATIONS

Table 1: List of Abbreviations

Abbreviation	Term
ACPAs	Antibodies to Citrullinated Protein Antigens
ACR/EULAR	American College of Rheumatology/ European League Against Rheumatism
AEs	Adverse Events
Anti-CCP3	Anti-cyclic citrullinated peptide-3
BMI	Body mass index
CDAI	Clinical Disease Activity Index
CL-RA	Clinically Apparent Rheumatoid Arthritis
CRF	Case Report Form
CSR	Clinical Study Report
CTCAE	Common Toxicity Criteria for Adverse Events
DAIT	Division of Allergy, Immunology, and Transplantation
DAS28-CRP	Disease Activity Score (28 joints) – C reactive protein
DMARD	Disease-Modifying Antirheumatic Drug
DSMB	Data and Safety Monitoring Board
EDC	Electronic Data Capture
EOS	End of Study
ESR	Erythrocyte Sedimentation Rate
FDR	First degree relative
GED	General Educational Development
HCQ	Hydroxychloroquine
HR	Hazard Ratio
hs-CRP	High-Sensitivity C-Reactive Protein
IA	Inflammatory Arthritis
IBW	Ideal Body Weight
ICH	International Conference on Harmonization
ID	Participant Identifier
IES	Intercurrent Event Strategy
IgM-RF	Immunoglobulin M – Rheumatoid Factor
IRB	Institutional Review Board

Autoimmunity Centers of Excellence
Statistical Analysis Plan – ARA08 StopRA

ITT	Intent-to-Treat Population
kg	kilogram
KM	Kaplan-Meier
LLN	Lower Limit of Normal
Max	Maximum
MDHAQ	Multi-dimensional Health Assessment Questionnaire
MedDRA	Medical Dictionary for Regulatory Activities
Min	Minimum
mITT	Modified Intent-to-Treat Population
mg	milligram
NCI	National Cancer Institute
NIAID	National Institute of Allergy and Infectious Diseases
NIH	National Institutes of Health
PLS	Population Level Summary
PP	Per Protocol Population
PRO	Patient Reported Outcome
PROMIS	Patient-reported Outcomes Measurement Information System
RA	Rheumatoid Arthritis
RAPID-3	Routine Assessment of Patient Index Data 3
RF	Rheumatoid Factor
SAEs	Serious Adverse Events
SAP	Statistical Analysis Plan
SD	Standard deviation
SDAI	Simple Disease Activity Index
SE	Shared Epitope
SOC	System Organ Class
SP	Safety Population
ULN	Upper Limit of Normal
WHO	World Health Organization
Y/N	Yes/No

2. PURPOSE OF THE ANALYSES

The purpose of this statistical analysis plan (SAP) is to describe the planned analyses and data displays to be included in the Clinical Study Report (CSR) for Protocol ARA08 StopRA. This document provides details on study populations, how the variables will be derived, how missing data will be handled and details on statistical methods to be used to analyze the safety and efficacy data.

The statistical analysis plan (SAP) is based on ICH guidelines E3 and E9 (Statistical Principles for Clinical Trials).

3. PROTOCOL SUMMARY

Title of the Protocol: Strategy to Prevent the Onset of Clinically-Apparent Rheumatoid Arthritis (StopRA)
ACE Protocol Number: ARA08
Protocol Chair(s): [name], MD, PhD
Sponsor: DAIT/NIAID/NIH
Objectives: The primary objective is to determine the efficacy of a 12-month course of hydroxychloroquine (HCQ) to prevent the development of clinically-apparent rheumatoid arthritis (RA) (as defined in Section 2.1, Primary Objective) at 36 months in subjects at high-risk for future RA due to high titer elevations of anti-cyclic citrullinated peptide-3 (anti-CCP3) (≥ 40 units) but who are without a history or clinical findings of inflammatory arthritis (IA) at Baseline. Secondary objectives include: 
1. To evaluate the safety of a 12-month course of HCQ in subjects who are at high-risk for development of RA.2. To evaluate the impact of HCQ on development of clinically-apparent RA (as defined in Section 2.1, Primary Objective) in high-risk subjects 12 months after initiation of study treatment.3. To evaluate the impact of HCQ on development of IA that may or may not meet criteria for RA in high-risk subjects 12 months after initiation of study treatment.4. To evaluate the impact of a 12-month course of HCQ on the timing of development of clinically-apparent RA over the entire study period.5. To evaluate the impact of a 12-month course of HCQ on the timing of development of IA, that may or may not meet criteria for RA, over the entire study period.6. To explore the relationship between baseline and evolving symptoms¹, risk factors² and the development of future clinically-apparent RA and response to HCQ.7. To evaluate the relationship between treatment with HCQ and amelioration of symptoms¹ of RA, and potential delay in onset of symptoms.8. To explore underlying immune responses over time in the early natural history of RA development and in response to HCQ therapy through measurement of a variety of biomarkers.
Study Arms: 
• Hydroxychloroquine: These subjects will receive 200 - 400 mg of HCQ (1-2 pills), based upon ideal body weight (IBW) at Screening, daily for 12 months.• Placebo: These subjects will receive 1-2 pills of placebo (based upon IBW at Screening) daily for 12 months.
Study Design: This is a phase 2 multi-center, randomized, placebo-controlled, double-blind, parallel group 36-month clinical trial to evaluate the effectiveness and safety of intervention with a 12-month course of HCQ to prevent the future onset of clinically-apparent RA (See definition in Section 2.1, Primary Objective). At screening, study subjects will be without IA, but will be at high-risk for developing future RA within the trial period as indicated by elevated anti-CCP3 antibodies that are ≥ 40 units (that is a level ≥ 2 times the normal cut-off of ≥ 20 units). Two-hundred eligible subjects will be randomized in a 1:1 ratio to receive either self-administered HCQ or placebo. Subjects will provide informed consent prior to any Pre-Screening or screening procedures. Subjects who are found to be eligible after the screening evaluation will return for a Baseline/Randomization visit within 30 days

¹ Baseline RA symptoms include self-reported joint pain, stiffness, and swelling, and overall fatigue.

² Risk factors include but are not limited to age, sex, genetic factors, socio-economic status, education, tobacco exposure, medications and medical hormone use, and dietary factors.

Autoimmunity Centers of Excellence
Statistical Analysis Plan – ARA08 StopRA

Title of the Protocol: Strategy to Prevent the Onset of Clinically-Apparent Rheumatoid Arthritis (StopRA)

of the initial screening visit. Subject eligibility will be confirmed prior to randomization. Eligible subjects will be randomized to receive either 200 - 400 mg (1-2 pills) of HCQ or 1-2 pills of placebo daily for 12 months based upon IBW at Screening. The weight-based dosing regimen for the study is outlined in Section 5.2, *Dosage Regimen*. Subjects will return to the study site for planned evaluations at Week 6, 12, 24, 36, and 52 (End of Treatment), and Months 18, 24, 30, and 36 (End of Study). During these study visits, subjects will have a joint exam and a physical examination. Study personnel will record the subject's interval medical history, assess adverse events, and collect samples for safety and mechanistic assessments (see Tables 6.1 & 6.2, *Schedule of Events*). Information on demographics (including socio-economic status and education), and other factors that may influence autoimmunity (e.g. tobacco exposure, hormonal status and exposures) may also be collected.

Site coordinators will call subjects at Week 18, 30, and 42 and at Month 15, 21, 27, and 33 to answer subject questions, update contact information, and to assess AEs/reactions, study drug dosing and pregnancy status (during the treatment period), and joint symptoms. If a subject indicates that he/she is experiencing joint symptoms suggestive of RA (that include new or worsening joint pain, stiffness or swelling since the prior study visit), or symptoms suggestive of an AE, the subject will be asked to return to the study site as soon as possible.

Visits and assessments for subjects who develop RA, IA with erosions, or who become pregnant prior to the Month 36 visits will be different from subjects who never develop RA. Details of these assessments may be found in protocol sections 6.5.9, *Evaluations Triggered by a Swollen Joint*, 6.5.10, *Procedures for Subjects Diagnosed with Inflammatory Arthritis or Rheumatoid Arthritis by an Outside Physician*, and 6.5.11, *Special Considerations for Pregnant Subjects*.

Endpoints:

The primary efficacy endpoint is the development of clinically-apparent RA by 36 months, where clinically-apparent RA is defined in Section 2.1, *Primary Objective*.

Secondary efficacy and safety endpoints are described in Sections 3.3.1, *Secondary Efficacy Endpoints*, and 3.3.2, *Secondary Safety Endpoints*.

Sample Size: 200 eligible subjects will be randomized in a 1:1 ratio.

Data Analyses: For the primary analysis, we are interested in demonstrating a long-term impact of a 1-year course of HCQ treatment on preventing the development of clinically-apparent RA (defined in Section 2.1, *Primary Objective*) in high-risk subjects. As such, rather than comparing full survival curves between treatment arms, the sample size for this study was selected to achieve sufficient power to compare survival curves at a fixed point 3 years after initiating treatment with HCQ.

All secondary analyses will be conducted in an exploratory fashion with p-values and confidence intervals presented as descriptive statistics with no adjustments for multiple comparisons. Tests will be two-sided and interval estimates will be generated at the 95% confidence level.

4. GENERAL ANALYSIS AND REPORTING CONVENTIONS

The following analyses and reporting conventions will be used:

- Categorical variables will be summarized using counts (n) and percentages (%) and will be presented in the form “n (%).” Percentages will be rounded to one decimal place.
- Numeric variables will be summarized using n, mean, standard deviation (SD), median, minimum (min), maximum (max).
 - The median, min and max will be reported at the same level of significance as the original data.
 - The mean will be reported at one more significant digit than the precision of the data.
 - SD will be reported at two more significant digits than the precision of the data.
 - The median will be reported as the rounded average of the two middle numbers if the dataset contains an even number of observations.
- Test statistics including t and z test statistics will be reported to two decimal places.
- P-values will be reported to three decimal places if greater than or equal to 0.001. If less than 0.001, the value will be reported as “<0.001.” A p-value can be reported as “1.000” only if it is exactly 1.000 without rounding. A p-value can be reported as “0.000” only if it is exactly 0.000 without rounding.

If departures from these general conventions are present in the specific evaluations section of this SAP, then those conventions will take precedence over these general conventions.

5. ANALYSIS POPULATIONS

Four analysis populations, the Intent-to-Treat (ITT), modified Intent-to-Treat (mITT), Per Protocol, and safety population will be defined for this study.

5.1. Safety Population

The safety population (SP), which will be used for all safety analysis, will include all participants for whom study treatment is initiated.

5.2. Intent-to-Treat Population

The Intent-to-Treat population (ITT) will include all randomized participants.

5.3. Modified Intent-to-Treat Population

The modified Intent-to-Treat (mITT) population will include all randomized participants who receive at least one dose of assigned study drug and meet entry criteria. The primary efficacy analyses will be based on the mITT population. Participants who, for whatever reason, do not complete their assigned therapy will be included in the mITT population in the groups to which they were randomized.

5.4. Per Protocol Population

The Per Protocol (PP) population will be defined as those participants in the mITT population who receive at least 80% of the assigned study treatment regimen with no substantive deviations from protocol procedures that would impact evaluation of efficacy.

A data review panel that will include the Protocol Chair ([name]) and participants from DAIT and Rho, Inc., will evaluate deviations from the protocol including, for example, violations of entry criteria, departures from assigned treatment regimen, use of prohibited therapy or HCQ prescribed outside of the study, failure to complete study visits, or to complete visits within the specified visit windows. The participant ID numbers will be replaced with randomly generated ID numbers for the PP population review.

The ARA08 study conducted an interim analysis in April 2022 as part of the regularly scheduled DSMB review. The Interim Statistical Analysis Plan is provided in Appendix 14.1. Due to the evidence of futility in the interim analysis results, the DSMB recommended that the ARA08 study stop early, and that the treatment assignments be released to the participants. Since the ARA08 study treatment assignments will be unmasked prior to database lock, the data review panel evaluation of the participants to include and exclude from the PP population will take place after the treatment assignments have been unmasked.

Levels of HCQ analyzed from serum samples taken during the study treatment period will not be used in the masked data review panel's evaluations of deviations from the protocol. The panel may exclude participants from the PP population if protocol deviations would be expected to impact the primary efficacy endpoint. Primary and secondary efficacy analyses may be replicated on the PP population.

6. STUDY PARTICIPANTS

6.1. Disposition of Participants

The disposition of all enrolled participants will be summarized in tables and listed. Enrollment is defined as participants who have signed the informed consent.

The numbers and percentages of randomized participants who qualify for each analysis population, completed study treatment and completed the study will be presented by treatment arm and overall. For participants who did not complete study treatment, the reasons for early discontinuation of study treatment will be presented by treatment arm. For participants who did not complete the study, the reasons for early termination of study participation will be presented by treatment arm.

6.2. Demographic and Other Baseline Characteristics

Summary descriptive statistics for baseline and demographic characteristics will be reported for the ITT, mITT and PP samples by treatment group. Characteristics to be summarized include:

- Age
- Race (White, Black, Asian, Native Hawaiian or Other Pacific Islander, American Indian or Alaska Native, Other/Unknown)
- Hispanic ethnicity (Hispanic, Not Hispanic)
- Jewish ethnicity (Jewish, Not Jewish, Unknown)
- Sex (Male, Female)
- Body Mass Index (BMI)
- Recruitment Method (First Degree Relative (FDR), Clinic Patient, General Population)
- Participant Has a FDR with RA (Yes/No)
- Smoking Status (Smoker, Non-smoker)
 - For current smokers, baseline pack years at the current level will be computed as:
The average # cigarettes per currently smoked * the average # years at this level
- Baseline Cigar Use (Yes/No)
 - Cigar Users: Average Cigars per Day
 - Cigar Users: Number of Years Used Cigars
- Baseline Tobacco Pipe Use (Yes/No)
 - Tobacco Pipe Users: Average Bowls per Day
 - Tobacco Pipe Users: Number of Years Used Pipes
- Baseline Chewing Tobacco or Snuff Use (Yes/No)
 - Chewing Tobacco or Snuff Users: Average Wads per Day

Autoimmunity Centers of Excellence
Statistical Analysis Plan – ARA08 StopRA

- Chewing Tobacco or Snuff Users: Number of Years Used Chewing Tobacco or Snuff
- Baseline Electronic Cigarettes Use (Yes/No)
 - Electronic Cigarettes Users: Electronic Cigarette Use Frequency (\leq 1 Day a Week, 2-4 Days a Week, \geq 5 Days a Week)
 - Electronic Cigarette Users: Number of Years Used Electronic Cigarettes
- Baseline Anti-CCP3 (units)
- Baseline Anti-CCP3 Positivity (Negative ($<$ Upper Limit of Normal (ULN), Low Positive (1.0 - $<$ 2.0 x ULN), Medium Positive (2.0 - $<$ 3.0 x ULN), High Positive (\geq 3.0 x ULN))
- Baseline IgM-RF (U/mL)
- Baseline IgM-RF Positivity (Negative ($<$ Upper Limit of Normal (ULN), Low Positive (1.0 - $<$ 2.0 x ULN), Medium Positive (2.0 - $<$ 3.0 x ULN), High Positive (\geq 3.0 x ULN))
- Baseline hs-CRP (mg/L)
- Baseline hs-CRP Positivity (\leq 3.0 mg/L, $>$ 3.0 mg/L)
- Baseline Shared Epitope (SE) Positivity (Negative on all epitopes and specific alleles (e.g. *0401, *0404, etc.), Positive on at least 1 epitope or specific allele)
- Baseline Shared Epitope Number of Positive Results (0, 1, 2, etc.)
- Baseline Pain Score
- Baseline Fatigue Score
- Baseline Morning Stiffness Duration
- Baseline Number of Tender Joints from Physician Joint Exam
- Baseline Disease Activity Score (28 joints) – C reactive protein (DAS28CRP)
- Baseline Routine Assessment of Patient Index Data 3 (RAPID3)
- Baseline Simple Disease Activity Index (SDAI)
- Baseline Clinical Disease Activity Index (CDAI)
- Baseline Patient-reported Outcomes Measurement Information System (PROMIS) Profile 29 Physical Health Score
- Baseline PROMIS Profile 29 Mental Health Score
- Baseline PROMIS Profile 29 Social Health Score

A listing of the demographic and baseline characteristics of randomized participants by treatment arm will be prepared.

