		18 JAN 2018						

ARA08: StopRA	REQUIRED Source Document	Manual of Procedures
Current Smokers		
3) On average, how many cigarettes per day do you currently smoke?	_____ cigarettes/day	
4) On average, how many years have you smoked at this level?	_____ years (Skip to Section 4)	
Past Smokers		
5) When did you permanently stop smoking?	_____ (month/year)	
6) On average, how many cigarettes did you smoke per day when you were smoking?	_____ cigarettes/day	
7) How many years in total did you smoke at that level?	_____ years	
Section 4: TOBACCO USE (EDC Page: Epidemiologic Questionnaire)		
QUESTION	ANSWER	
1) Have ever used any other form of tobacco (besides cigarettes)?	 Yes (Continue)  No (Skip to Section 5)	
Cigars		
2) Do you smoke cigars?	 Yes (Continue)  No (Skip to Pipes)	
3) On average, how many cigars do you smoke per day?	_____ cigars/day	
4) How many years have you used cigars?	_____ years	
Pipes		
5) Do you smoke a pipe?	 Yes (Continue)  No (Please skip to Chew/Snuff)	
6) On average, how many bowls do you smoke per day?	_____ bowls/day	
7) How many years have you used pipes?	_____ years	
Chew/Snuff		
8) Do you use chew/snuff?	 Yes (Continue)  No (Skip to Electronic cigarettes)	
9) How many wads of chew/snuff do you use per day?	_____ wads/day	
10) How many years (in total) have you used chew/snuff?	_____ years	

ARA08: StopRA	REQUIRED Source Document	Manual of Procedures
Electronic Cigarettes (e-cigarettes or 'vaping')		
11) Do you use electronic cigarettes?	 Yes (Continue)  No (Skip to Section 5)  One day a week or less  2 to 4 days a week  5 or more days a week (Continue)	
12) If yes, how often are you using electronic cigarettes?	 One day a week or less  2 to 4 days a week  5 or more days a week (Continue)	
13) How many years (in total) have you used e-cigarettes?	_____ years	
Section 5: EXPOSURE TO TOBACCO SMOKE (EDC Page: Epidemiologic Questionnaire)		
QUESTION	ANSWER	

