- Baseline self-reported fatigue
- Baseline CDAI
- Baseline SDAI
- Baseline RAPID-3
- Baseline DAS28-CRP

Autoimmunity Centers of Excellence
Statistical Analysis Plan – ARA08 StopRA

- Baseline PROMIS Profile 29 Physical Health Score
- Baseline PROMIS Profile 29 Mental Health Score
- Baseline PROMIS Profile 29 Social Health Score
- Baseline Anti-CCP3 (units)
- Baseline Anti-CCP3 Positivity (Negative (< Upper Limit of Normal (ULN), Low Positive (1.0 - <2.0 x ULN), Medium Positive (2.0 - <3.0 x ULN), High Positive (\geq 3.0 x ULN))
- Baseline IgM-RF (U/mL)
- Baseline IgM-RF Positivity (Negative (< Upper Limit of Normal (ULN), Low Positive (1.0 - <2.0 x ULN), Medium Positive (2.0 - <3.0 x ULN), High Positive (\geq 3.0 x ULN))
- Baseline hs-CRP (mg/L)
- Baseline hs-CRP Positivity (\leq 3.0 mg/L, $>$ 3.0 mg/L)
- Baseline age (years)
- Sex (male/female)
- BMI
- Baseline Shared Epitope (SE) Positivity (Yes, No)
- Baseline Shared Epitope Number of Positive Results (0, 1, 2)
- Participant has a FDR with RA (Yes, No)
- Salary level (< \$50,000; \$50,000 - < \$75,000; \geq \$75,000)
- Highest education level achieved (up to High School/GED, College, Graduate School)
- Tobacco exposure
 - Smoking status (Never smoked, Former smoker, Current smoker)
 - Baseline Pack Years at Current Level for Smokers
 - Years as Adult Living with Smoker
- Baseline Medications
 - Statin use (Yes/No)
 - Medical hormones (Yes/No)

Each fixed effect will be evaluated for its impact on the time to development of CL-RA by fitting a Cox proportional hazards model with independent variables for treatment arm, risk factor and treatment arm * risk factor interaction. The risk factors with significant p-values for the Wald chi-square test statistic, along with significant interaction terms, will be included in the final Cox proportional hazards model.

8.3.6. Study Objective 7

Study Objective 7 is to evaluate the relationship between treatment with HCQ and amelioration of symptoms of RA, and potential delay in onset of symptoms. RA symptoms include self-reported joint pain, stiffness, and swelling, and overall fatigue. The clinical endpoint to evaluate this objective will be the self-reported joint symptom counts assessed at each clinic visit.

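### SAP 6.2 defines pack-years without dividing by cigarettes per pack; programmed as written, the variable would be cigarette-years, 20 times pack-years at 20 cigarettes per pack.

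*SAP*

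**What the plan says.** In the list of baseline characteristics, SAP 6.2 introduces the derivation with "For current smokers, baseline pack years at the current level will be computed as" and then gives the formula: "The average # cigarettes per currently smoked * the average # years at this level". There is no divisor, and the unit after 'per' is incomplete.

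The inputs come from the baseline epidemiologic questionnaire (Protocol Appendix 15.5.4.1, smoking history, items for current smokers). The two relevant items are "On average, how many cigarettes per day do you currently smoke" and "On average, how many years have you smoked at this level". The first is answered in cigarettes per day, the second in years.

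The variable appears again in SAP 8.3.5 (Study Objective 6), where "Baseline Pack Years at Current Level for Smokers" is listed under tobacco exposure among the candidate risk factors for the Cox models of time to clinically-apparent RA. Neither document collects packs per day, states a pack size or gives another definition of pack-years.

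**The concern.** A pack-year is a pack a day for one year, so a count of cigarettes has to be converted to packs before it is multiplied by years. The SAP formula omits that step, and its label and its unit disagree.

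Section 2 of the SAP says that the document sets out how variables are derived, so a programmer and an independent validator who both follow it would agree on the same wrong value. Two outputs depend on it. One is the baseline summary by arm for the ITT, mITT and PP samples, together with the participant listing. The other is Objective 6, whose population-level summary (SAP Table 13) is the hazard ratio with its 95% confidence interval for each potential risk factor. A hazard ratio read as per pack-year would in fact be per cigarette-year, a much smaller step.

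**Working it through.** The documents give no numerical pack-years value, so there is no figure to reproduce. The check is one of units, followed by its consequence for the Cox model.

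**Inputs**
- *c* = cigarettes per day currently smoked (Protocol Appendix 15.5.4.1)
- *y* = years smoked at that level (same place)
- *k* = cigarettes per pack. Not stated in the documents; assumed to be 20, with 10 and 25 shown as a range.

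**Formulas**
- SAP 6.2 as written: *c* × *y*, in cigarettes/day × years
- Pack-years: (*c* / *k*) × *y*
- Ratio of the two: *k*, whatever the smoking history

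**Values**

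| Cigarettes/day | Years | SAP 6.2 as written | Pack-years, k = 20 | k = 10 | k = 25 |
|---|---|---|---|---|---|
| 10 | 10 | 10 × 10 = 100 | 100 / 20 = 5 | 10 | 4 |
| 20 | 10 | 20 × 10 = 200 | 200 / 20 = 10 | 20 | 8 |
| 20 | 30 | 20 × 30 = 600 | 600 / 20 = 30 | 60 | 24 |

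The inflation is 20-fold at 20 per pack, and 10-fold or 25-fold at the other two sizes. Some divisor is needed in every case.

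**Effect on the Objective 6 hazard ratio**

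Let *P* be true pack-years and *X* = 20*P* the variable as written. The log hazard is the same function of exposure, so β_X = β_P / 20 and HR_X = HR_P^(1/20). For illustrative hazard ratios per pack-year (the documents give none):
- 1.01^(1/20) = 1.0005
- 1.02^(1/20) = 1.0010
- 1.05^(1/20) = 1.0024

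The confidence limits shrink towards 1 in the same way.

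**Effect on tests and selection**

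The standard error is divided by 20 along with the coefficient, so the Wald ratio is unchanged: (β_P / 20) / (SE_P / 20) = β_P / SE_P. The same holds for the treatment-by-exposure interaction term. SAP 8.3.5 keeps risk factors at p < 0.1 and interactions at p < 0.05, so no term enters or leaves the model because of the scale.

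**The case against.** The best reply is that the line is visibly incomplete. With a word gone after 'per', it is weak evidence of the derivation intended, and the label shows that pack-years were meant. A competent programmer would probably insert the conversion, and values such as 600 would stand out at table review. Whether the missing word was lost in the source or in conversion to text cannot be settled from the text alone.

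Part of this stands. The documents describe a plan and contain no computed pack-years, so the error is conditional on literal programming. But restoring 'day' does not supply a divisor: the formula then reads as a complete product of the two questionnaire items. The compliance formula in SAP 7.4 came through conversion with its fraction intact. A derivation rule should not depend on someone noticing that it is wrong.

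It is also fair to say that the reach is small. The variable covers current smokers only. The same constant applies in both arms, so the relative comparison between them is preserved. The primary estimand and its sensitivity estimands (SAP 8.2.2 and 8.2.3) do not use it. The Objective 4 and 5 Cox models adjust for site and recruitment method, not for pack-years.

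Three stronger readings may occur to a reader, and the documents do not support them:
- *The trial's reported smoking values are wrong.* Neither document reports any.
- *A minimization factor is affected.* Protocol 3.1.1 and SAP 7.2 minimized on smoker versus non-smoker; pack-years played no part in treatment assignment.
- *The smoking effect would be lost.* Only the displayed per-unit hazard ratio moves close to 1; the test and the selection decision stay the same. Nor would every value look absurd: 3 a day for 10 years gives 3 × 10 = 30, which is wrong (1.5 pack-years at 20 per pack) but plausible.

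**Conclusion.** The definition is wrong as written: a variable labelled pack-years is specified as cigarettes times years. If the line is followed literally, baseline values for current smokers would be inflated by the number of cigarettes per pack, 20-fold under the usual convention. The hazard ratio and confidence interval for one exploratory Objective 6 covariate would be expressed per 1/20 of a pack-year.

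The conclusion rests on three things: reading the missing word as 'day', which the questionnaire items support; a pack size of 20, which is an assumption and sets only the size of the factor; and programming that follows the SAP text. This is a minor correction to a derived variable. Its consequences stop at a descriptive summary, a listing and the scale of one covariate estimate.

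**What to change.** In SAP 6.2, define the variable as (average number of cigarettes per day currently smoked / 20) × average number of years at this level. State that a pack is taken as 20 cigarettes, and restore the word 'day'. Alternatively, keep the product and rename the variable cigarette-years in both SAP 6.2 and SAP 8.3.5, so that the hazard ratio is read on the right scale.

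The cost is one line in the SAP and one in the derivation program; no new data are needed. If the database is already locked, Protocol 8.5.5 provides for recording the change in the clinical study report. Any smoking table or Objective 6 output already produced should be checked against the corrected definition.
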